PLWH can be powerful change agents for HIV prevention within communities. Our research suggests that as PLWH receive ART and restore their health, they are motivated to protect their social network members and engage in prevention advocacy (i.e., encourage friends and family to seek HIV testing and care and reduce HIV risk); however, the quality of this advocacy is hampered by challenges related to message content, style and timing of delivery, and the selection of appropriate recipients for advocacy. With effective advocacy training, mobilizing PLWH to be change agents within their networks has the potential to be a “game changer” for HIV prevention, particularly in high-prevalence settings where virtually every family is touched by HIV. In the proposed research, we will conduct a randomized controlled trial (RCT) of *Game Changers*, an 8-session peer-led group intervention that aims to empower and mobilize PLWH to be agents for HIV prevention in their social networks. By decreasing stigma among PLWH and their social network members, as well as training PLWH on key strategies to engage social network members in discussions around HIV, *Game Changers* provides PLWH with the tools to do prevention advocacy and is facilitated by peers who are from participants’ communities and living with HIV. *Game Changers* was developed through an NIMH-funded R34 in partnership with the Infectious Diseases Institute (IDI), a public-private partnership in Kampala that provides care to PLWH, that trains healthcare workers on HIV care and treatment, and conducts research to address the HIV epidemic. As part of the intervention development process, the team conducted focus groups with PLWH and social network members, and engaged with community stakeholders, including a community advisory board. Our pilot RCT with 98 PLWH and 57 social network members revealed promising preliminary intervention effects on reduced internalized stigma and increased HIV-serostatus disclosure to social network members among PLWH, as well as increased condom use and HIV testing among social network members.

The **Specific Aims** are:

1. To conduct a fully powered RCT of *Game Changers* to test intervention effects on the primary outcomes of increased HIV testing, reduced condomless sex, and decreased enacted HIV stigma among social network members of participating PLWH.

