Aims 1-3. Primary analyses will use a standard intent-to-treat approach, applying generalized mixed models (linear for continuous outcomes; logistic for binary outcomes) to the repeated-measures data to examine how intervention effects change over time, using an indicator for study arm, timepoint (baseline vs. follow-up), and timepoint by arm interaction to indicate whether change differs between arms. Our statistical methods will be consistent with advances in the analysis of personal network research,^{66, 135-137} accounting for any correlation among participants in the same intervention group sessions, and among alters referred by the same PLWH (ego), by adjusting standard errors for statistical inference tests with a sandwich estimator as implemented in SAS v 9.4.^{96, 138-141} We will use imputation for item nonresponse and account for non-random dropouts using logistic regressions that assign weights to retained participants that are inversely proportionate to the predicted probability of the participant being retained; if dropout is random, analyses will incorporate design effects. In follow-up analyses, we will explore interactions between each potential moderator and arm, including sex (of ego and/or alter, and concordance between the two) to examine if these variables moderate the intervention effects. If interactions with categorical moderators are significant, we will conduct post-hoc simple main effects t-tests with Bonferroni corrections. For continuous moderators,¹⁴² we will graph significant interactions at low and high levels of each score (± 1 SD). We will conduct post-hoc simple main effects t-tests with Bonferroni correction by comparing differences between discrete points on the regression lines. If *Game Changers* shows significant effects on hypothesized mediators (Aim 3), to test mediation we will compare: (a) Aim 1 models, adding baseline measures of mediator(s); and (b) the same models as in (a), adding post-intervention measures of mediator(s).¹⁴³ We will examine whether including post-intervention mediator(s) in (b)

decreases the coefficient for intervention effects on outcomes relative to the corresponding coefficient from (a). We will use a bootstrapping approach to test whether mediators account for effects.^{144, 145}

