Statistical Power. We calculated power for alter reports of condomless sex at month 18. Based on the pilot, we assume 65% of control alters will report condomless sex at month 18. Starting with 736 alters, and assuming ~15% attrition by month 18 (which is conservative, based on 98% alter retention over 8 months in the pilot, and <10% attrition over 12 months in our other studies in Uganda), we will have 625 alters; accounting for within-ego clustering gives us an effective sample size of 612 for ICC=.01 or 568 for ICC=.05. For ICC=.01, we will have .80 power to detect a group difference of 10.3% (i.e., an intervention rate of 54.7%), and for ICC=.05, we will have power to detect a 10.7% group difference. These differences represent small effect sizes (Cohen's $d = .23\text{--}.24$). For PLWH index participants, using pilot data, we estimate the ICCs of our secondary outcomes to be small-to-moderate (0-.16), and assume 15% attribution and 7 intervention groups (either Game Changers or attention control), with an average cluster size of 12.9 (90 intervention participants/7 groups).^{96, 140, 141} After accounting for within-group correlations, we will have 80% power to detect medium to large differences (.41-.58 SD, based on the outcome) between the study arms at follow-up.

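### Aim 1 has three primary outcomes of equal standing, and the plan gives no testing order, success rule or multiplicity adjustment for them

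*Combined protocol and SAP*

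**What the plan says.** The Specific Aims describe a fully powered trial whose Aim 1 covers the "primary outcomes of increased HIV testing, reduced condomless sex, and decreased enacted HIV stigma" among network members. None is ranked above the others.

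Statistical Analysis (Aims 1-3) fits one mixed model per outcome and takes the arm-by-timepoint interaction as the intervention effect. Timepoint is described only as baseline against follow-up, although assessments take place at months 6, 12 and 18. The section gives no significance level, testing order, split of alpha, or rule on how many primary outcomes must succeed. Its only multiplicity control concerns moderators: if an interaction with a categorical moderator is significant, "we will conduct post-hoc simple main effects t-tests with Bonferroni corrections", with the same correction for continuous moderators.

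Statistical Power treats one alter outcome: "We calculated power for alter reports of condomless sex at month 18". HIV testing and enacted stigma have no power statement. Aim 4 also uses alters' condomless intercourse as its measure of effectiveness. Neither section calls condomless sex the single or first-tested primary outcome.

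**The concern.** The three outcomes serve one aim, and nothing written in advance says what counts as success on it. After the data are seen, an Aim 1 claim could rest on whichever outcome reached significance, and nothing in the plan would rule that out. Each extra test at an unadjusted level adds another chance of a false finding. The plan already accepts the need to correct for multiple tests in exploratory contrasts but leaves its confirmatory tests uncorrected. At stake is how far a single significant primary result can be relied on as evidence that the programme changes network members' behaviour or attitudes.

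**Working it through.** **Inputs from Statistical Power.** "we assume 65% of control alters will report condomless sex at month 18". "Starting with 736 alters, and assuming ~15% attrition by month 18", so 736 × 0.85 ≈ 625 alters. Then "effective sample size of 612 for ICC=.01 or 568 for ICC=.05". The stated results are "we will have .80 power to detect a group difference of 10.3% (i.e., an intervention rate of 54.7"%) for ICC .01 and, for ICC .05, "we will have power to detect a 10.7% group difference". Allocation is 1:1 (Randomization).

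**1. Effective sample size.** With m = 625/210 = 2.98 alters per index participant and design effect 1 + (m − 1) × ICC:
- ICC .01: 625/1.0198 = 612.9
- ICC .05: 625/1.0988 = 568.8

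Both agree with the plan.

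**2. Which alpha did the power calculation use?** The plan states none. The pooled two-proportion formula, with n per arm, is

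power = Φ{[Δ√n − z(1−α/2) √(2p̄q̄)] / √(p₁q₁ + p₂q₂)}

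- 65% to 54.7%, n = 306, two-sided 5%: [0.103 × 17.49 − 1.96 × 0.6933]/0.6894 = 0.643, power 0.740. The stated 0.80 is not reproduced.
- 65% to 54.3%, n = 284: power again 0.740.
- 65% up to 75.3%, n = 306: [0.103 × 17.49 − 1.96 × 0.6472]/0.6430 = 0.829, power 0.797.
- 65% up to 75.7%, n = 284: power 0.799.

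The plan's 10.3 and 10.7 points therefore reproduce as increases from 65%. Solving those for alpha at 0.80 power gives 0.0514 and 0.0505, which points to an unadjusted two-sided 5%. For a reduction, the 80%-power detectable differences are 11.1 points (612) and 11.5 points (568). These are the baselines used below.

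**3. Family-wise error, three tests at two-sided 5%.** Independent tests give 1 − 0.95³ = 14.3%, and the upper bound at any correlation is 3 × 5% = 15%. Counting only the favourable direction, 1 − 0.975³ = 7.3% against 2.5% for one test. For correlated tests, 2,000,000 draws of three equicorrelated normal statistics gave:

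| Correlation | Any false significant result | False claim of benefit |
|---|---|---|
| 0 | 14.3% | 7.3% |
| 0.3 | 13.6% | 6.8% |
| 0.5 | 12.5% | 6.3% |
| 0.9 | 8.4% | 4.2% |

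The documents give no correlation. Low to moderate values are plausible because HIV testing is assessed only in alters of negative or unknown serostatus (Individual-Level Outcomes), and enacted stigma is reported by the index participant rather than the alter (Network Composition).

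**4. Cost of adjustment for condomless sex.** At Holm's strictest step, 0.05/3:
- Effective n 612: detectable reduction 11.1 → 12.9 points
- Effective n 568: detectable reduction 11.5 → 13.4 points
- Power for 65% to 54.7% at 612: 0.740 → 0.582

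In a fixed sequence led by condomless sex, that outcome keeps the full 5% and its power does not change.

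**The case against.** Three objections carry weight.

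First, the outcomes may be separate hypotheses. Aim 3 gives them different pathways (advocacy for testing and condom use, disclosure for stigma), and they differ in population and reporter. Whether distinct hypotheses need family-wise control is partly convention. But that position has to be declared beforehand, and the plan instead groups the outcomes under one aim.

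Second, no success rule is written, so it is an inference that any one outcome would suffice. If all three had to succeed, no adjustment would be needed. This stands as a condition on the figures; the missing rule is itself the gap.

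Third, a fixed order led by condomless sex is not the only reasonable one. Aim 1 lists HIV testing first, and the assessment overview ties the six-month interval to testing guidance. Condomless sex has about 0.74 power at the protocol's own effect, so a real testing effect placed second would lose confirmatory status about one time in four (1 − 0.74 = 0.26). The order is for the investigators to choose.

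A reader might also infer that an ineffective programme has a one-in-seven chance of being declared effective and carried forward to roll-out. The documents do not support that. The 14.3% counts significant results in both directions, including harm; false claims of benefit run at about one in 14. Community Engagement ties dissemination to cost-effectiveness, and Aim 4 builds that analysis on condomless intercourse alone, so a chance finding on testing or stigma would not by itself lead to roll-out.

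**Conclusion.** The point holds: the confirmatory family under Aim 1 has no error control, although exploratory contrasts do. The chance of at least one false significant result is about 12.5% to 14% for correlations of 0.5 down to 0, falling to 8.4% at 0.9. For false claims of benefit it is about 6% to 7% against a nominal 2.5%. These figures assume two-sided 5% per test (implied by the power calculation, not stated), a claim of success on any one outcome, and one contrast per outcome. If months 6, 12 and 18 were tested separately, the rates would be higher. The plan should be changed, and the change needs no new data.

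**What to change.** Add to Statistical Analysis, Aims 1-3:

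> The three Aim 1 outcomes form one confirmatory family. Each is tested by a single prespecified arm-by-time contrast from baseline to month 18. Family-wise error is held at two-sided 5% by [Holm's procedure / a fixed sequence in the order …], set before any outcome is compared between arms. Other time points are supportive and are reported with confidence intervals.

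Month 18 matches the power calculation and must apply to all three outcomes; fixing it for condomless sex alone would leave the others open to a choice of visit. If a fixed sequence is preferred, condomless sex first fits the only alter power calculation and the Aim 4 outcome, and leaves its alpha intact.

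The text costs a few sentences. Under a fixed sequence, every outcome after the first non-significant one becomes supportive only. Holm avoids that dependence on order, at the price of the larger detectable differences in step 4 of the working. Whichever is chosen, the power statement should start from 11.1 and 11.5 points for a reduction, not 10.3 and 10.7.

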
Game Changers Pilot. We developed and conducted a pilot study of *Game Changers* at IDI, the proposed study setting. We engaged community members on IDI's community advisory board (CAB) and the National Forum of People Living with HIV/AIDS Networks in Uganda (NAFOPHANU), to obtain input throughout the study, and in the development of this proposal (see letters of support).

Initial Formative Research (R24 HD056651, R21 MH087249). [name] and [name] conducted studies documenting prevention advocacy among PLWH in Uganda. All PLWH reported encouraging at least one alter (friends, family, partners, etc.) to engage in protective behaviors.^{27, 28, 79, 80} However, much advocacy involved only general cautionary messages about HIV, rather than advocating specific protective behaviors, highlighting the potential for training to improve advocacy quality. Prevention advocacy was associated with lower internalized stigma, more disclosure, and more condom use, ART adherence, and HIV care engagement, consistent with our conceptual framework (Fig. 1). The study also found that participant reports of alter characteristics had a 70-90% accuracy rate comparing respondent assessments against alter reports, in terms of PLWHs' perceptions of alters' HIV status (89%), HIV care engagement (86%), and ART use (71%).^{81, 82}

Focus Groups on Intervention Acceptability (R34MH111460). We used the above formative research results as the basis for developing *Game Changers*. In an R34 led by [name], the team conducted 6 focus groups of PLWH (n=31) and 2 focus groups of social network members to whom they disclosed (family, friends; n=16). Participants (24 women, 23 men) were recruited at IDI's HIV clinic. We found high anticipated acceptability for *Game Changers*: both PLWH and social network members were enthusiastic about the program. Participants liked that the program would help them build skills; they were motivated to have conversations about HIV but did not know how to initiate them. They also felt that the program could help to reduce HIV stigma in their communities. As one PLWH said, "...when we approach [them], it is really difficult to talk to them because you are scared... this program will help us get the techniques on how to approach the people"; a social network member said, "...if you are trained you can learn how to start [conversations on HIV] and then you build from that, but starting is always hard." Another social network member said: "... people have a way they perceive HIV positive people, they stigmatize, neglect them... it is hard so I would like if I get a chance to talk to the HIV positive and negative people and show them that positive people are also humans."

We used the focus group results to develop the intervention. We integrated examples of conversation starters and stigmatizing and supportive reactions to HIV conversations that came up in the focus groups in the intervention manual, as role plays and examples of situations that participants might encounter in their social network. Participants described ideal characteristics of intervention facilitators, including being HIV-positive; having experience as a counselor with a strong ability to communicate clearly and create a supportive environment; and having HIV-related medical knowledge. There were differing opinions regarding the need for groups to be single or mixed sex; therefore, in the pilot (described below) we conducted two same-gender and two mixed-gender groups, and found the mixed gender groups to be highly acceptable; participants spoke of wanting to learn advocacy skills to use in their entire network, not only skills that were relevant for one gender.

*Game Changers Pilot RCT.*⁸³ 98 PLWH and 57 alters participated in the pilot RCT across four intervention-control cohorts (with a wait-list control group).⁸³ The pilot intervention was the same as the intervention outlined below for the proposed study. Participants were interviewed at baseline and ~5-months and ~8-months post-baseline. Results showed high feasibility, acceptability, and preliminary effects, consistent with our conceptual model. In terms of feasibility, of the 98 participants recruited (51 intervention, 47 control), 97 (99%) and 93 (95%) completed assessments at months 5 and 8, demonstrating very high retention. Retention was also high in intervention sessions, with 60% of the intervention group attending all sessions and each session attended by an average of 76% of participants. Reasons for missed sessions included being out of town, conflicting work/school schedules, sick or caring for someone sick, moved, and transportation issues.

To test the feasibility of recruiting alters, we asked each of the 98 PLWH to refer up to 3 alters; 214 alters were referred by 89 (91%) PLWH (average of 2.3 alters (out of max. of 3) referred by each, suggesting little difficulty in identifying alters to recruit). However, since alter recruitment was added post-hoc to the study design (and with no designated funding in the budget), we decided to try to contact only 135 alters. Of the 135 alters, 17 (13%) were already enrolled (15 as PLWH, 2 as alters) and thus were ineligible, and 1 was withdrawn. Of the remaining 117, 34 (29%) could not be reached (did not answer the phone or had a nonworking number); and 26 (22%) declined because they were busy, lived far, or were sick. Thus, 57 alters (49%) were enrolled; 35 from intervention participants and 21 from control participants. The characteristics of the recruited alters (61% female, 32% family, 68% friends, 14% sex partners; 43% HIV+) were similar to that of all alters listed in the index participant networks (53% female, 37% family, 63% friends, 4% sex partners; 28% HIV+), which increases confidence that the recruited alters represent the larger network. We did not repeatedly

try to contact alters, nor incentivize enrollment with alternative forms of assessment (e.g., phone, home visit, etc.). In the proposed study, we will have resources to hire staff to focus on alter interviews, and to make multiple call attempts, interview alters by phone, reimburse alters for transport, and travel to interview alters outside of Kampala; plus, unlike in the pilot, in the proposed study when an alter is unable to be reached, we will ask the index participant to refer additional alters for us to contact. With these changes, we expect a much higher rate of alter recruitment in the proposed study; nonetheless, our recruitment and power analysis procedures accounted for a potential 50% enrollment rate of referred alters.

Post-session feedback forms and post-intervention focus groups with intervention participants and facilitators indicated high acceptability. On individual session feedback forms, on a scale of 1 (*did not like at all*), to 5 (*liked very much*), average ratings were 4.7 (SD = 0.5), across all sessions. In the focus groups, participants reported very positive attitudes toward the intervention, highlighting the skills they learned for HIV serostatus disclosure, as well as the content on stigma. Participants reported that they increased their disclosure and prevention advocacy, especially on condom use and HIV testing. For example, a participant said, *"This training has given me the confidence to face someone and disclose to them that am HIV positive and advise them to go for testing and if found positive I encourage them to start on medication immediately. Personally, I used to fear... now I can take all my drugs openly without any fear."* Participants also said the intervention helped them to live positively and improve their own ART adherence, while also learning how to support other PLWH to do the same. Uniformly, the three facilitators enjoyed the intervention and said they saw participants improve: *"Those who came back and reported that they had disclosed to a, b, c, they had talked to somebody about HIV relating their own stories. So, to me that was a very good experience that the participants had taken so passionately to share and take on this prevention advocacy aspect."* Participants also requested additional skills building for supporting social network members who recently tested positive: *"Everyone gets scared when they are hit with the news that they are positive. So, when I talked and convinced my friend and he checked his status, he found out that he was positive, so how do I counsel him?"* Facilitators suggested strengthening the content around testing in terms of preparing alters for the test and supporting them afterward. They also suggested referring alters to get tested at the IDI clinic, where the intervention is conducted, so that that alter testing and linkage to care could be tracked through medical records.

The intervention showed preliminary effects consistent with hypotheses. Among alters at month 5, condomless sex with main partners in the past month decreased by 7.7% (46.2% to 38.5%) in the intervention group vs. an increase of 10.5% (57.9% to 68.4%) in the control group; this was a large effect (Cohen's $d = .76$), despite marginal statistical significance in this underpowered small pilot [OR (95% CI)= 0.3 (.1-1.2), $p=.08$]. Among the 20 alters who were HIV-negative prior to the 5-month follow-up and who were not tested for HIV between baseline and the 5-month follow-up, 5 of 15 intervention alters (33.3%) vs. 1 of 5 control alters (20.0%) reported being tested for HIV post-intervention (in between 5- and 8-month follow-ups), which represents a small-to-medium effect size (Cohen's $d = .30$). In terms of mediators, alters of intervention participants were significantly more likely to report engaging in prevention advocacy discussions (mainly on HIV testing, condom use, and ART) in their social networks ($p=.04$). Note that, because we only interviewed a small number of alters for feasibility rather than to detect effects, we did not interview all alters with whom the PLWH did prevention advocacy, and PLWH did not do prevention advocacy with all alters interviewed. Thus, we would expect effects to be stronger in the proposed study, in which we will recruit a larger number of alters.

Results for PLWH also showed effects consistent with hypotheses. Compared to controls at baseline vs. follow-up, intervention participants were more likely to report engaging in prevention advocacy [b (SE) = 0.4 (0.2), $p = .017$], especially related to HIV testing, condom use, and number of partners (all $p < .05$). Intervention participants were less likely to feel internalized [b (SE) = -0.3 (0.1), $p = .012$] and anticipated HIV stigma [b (SE) = -0.5 (0.2), $p = .011$], and to have concerns about disclosure [b (SE) = -0.3 (0.1), $p = .028$], and were ten times more likely to have disclosed to a main partner [OR (95% CI) = 10.0 (1.5-67.7), $p = .022$], compared to control participants. Moreover, intervention participants were more likely to report that all of their alters had been tested ($p < .10$), and that they disclosed to a greater proportion of alters ($p=.05$). The intervention also had effects on social network structure: intervention participants' networks became denser over time, with more and stronger connections among alters [b (SE) = 0.1 (0.3), $p = .004$].

Summary of Preliminary Studies. The team is well-positioned to conduct this RCT, with a great deal of expertise in the proposed study content and methods, and the demonstrated feasibility, acceptability, and preliminary efficacy of *Game Changers*. Based on our pilot, we changed intervention content and methods for the proposed RCT, some of which we already tested for feasibility with the pilot wait-list control group. As requested by pilot participants in the post-intervention focus groups, we added content, practice, and

instruction on social network mapping and more opportunity for prevention advocacy practice (e.g., role plays on HIV stigma and pre-and post-HIV testing support). We also added content related to PrEP (e.g., information about PrEP, and role plays and strategies about how to do prevention advocacy around PrEP), given increased availability in Uganda, especially for key and priority populations (e.g., sero-discordant couples). However, since PrEP access is still limited and not available for all, we will examine it as a secondary outcome only. As noted above, we will modify alter methods, to employ more staff to track alters, ask staff to travel to alters who live away from Kampala, and provide a higher incentive (e.g., for transportation costs); we will also conduct interviews with alters by phone. These revised procedures should decrease the number of alters who decline (or who are not referred) because they live far away or are too busy to come to the site (~20% of the alters referred in the pilot). Nonetheless, we will plan for a 50% alter enrollment rate and ask PLWH to refer up to 7 alters (up from 3 in the pilot), with a target of enrolling an average of 3.5 (and no more than 4/participant).

Study Methods

[figure not shown]
Setting. The study will be conducted at IDI, which provides outpatient HIV care to ~8,000 active patients and conducts HIV-related clinical trials. Luganda is the native language, but people with a secondary education often speak English, and all clinic staff are fluent in English.

Community Engagement. We will partner with two community stakeholder groups, as in the pilot (see letters of support): IDI's community advisory board (CAB) and the National Forum of People Living with HIV/AIDS Networks in Uganda (NAFOPHANU), to obtain input at critical study points 1-2 times/year on the assessment, intervention content (e.g., updates/ resources for HIV prevention), interpretation of results, and next steps for intervention dissemination, if it is shown to be cost-effective. IDI's CAB and NAFOPHANU have ~20 members each from diverse community groups (e.g., clergy, activists, youth leaders, expert patients). Notably, for the pilot, NAFOPHANU disseminated the facilitator job ad, and the facilitators were NAFOPHANU members. Members of both groups will receive transport costs and refreshments for each meeting.

Intervention Content and Structure. The intervention component of the study, including developing and finalizing the intervention manual, and oversight of facilitator training and supervision, will be led by [name] (MPI). The Facilitator Manual, available in English and Luganda, was iteratively revised in the pilot based on feedback from the CAB and NAFOPHANU, and focus groups with participants and facilitators (see Preliminary Studies). The intervention consists of 8 sessions (first 4 are weekly, and last 4 are every two weeks) over three months. Internalized stigma reduction and self-acceptance, comfort and competence with HIV disclosure, compassion for oneself and others, and healthy, positive living, form the foundation for effective prevention advocacy, and thus are the focus of the first 3 sessions (see Fig 1 and Table 1). **Session 1** uses compassion-focused therapy principles³⁶⁻³⁹ and cognitive behavior therapy strategies developed in [name]'s prior intervention research³⁵ to break down internalized stigma and build peer support and solidarity, setting the stage for the remaining sessions by introducing the overall vision for empowering PLWH to become change agents for HIV prevention. With participants feeling more confident and supported, **Session 2** emphasizes the need for self-compassion and empathy when making disclosure decisions, and focuses on building HIV disclosure decision-making skills, knowing whom to disclose to and when, and how to initiate and navigate disclosure conversations. **Session 3** focuses on building skills and motivation for healthy, positive living so that

[figure not shown]
advocates' own behavior (e.g., condom use, adherence) is consistent with the behavior they encourage in others; participants also receive basic HIV information and learn how to address common HIV myths. Session 3 also introduces the concept of social networks, and how knowledge about one's own social network can help to make disclosure and advocacy decisions. **Session 4** begins the advocacy training. Participants use a novel method (developed in our pilot) to map their social network to determine "strategic alters" (see Fig. 2).⁸⁴ Participants are given a "bulls-eye" handout and 20 post-its (Fig. 3). They list the nicknames or initials of up to 20 alters (10 to whom they are close and 10 to whom they are less close, using differently colored post-its), and then put check-marks on the post-its of alters to whom they have disclosed, and stars on the post-its of alters with whom they have discussed HIV. Next, participants place the post-its on the bulls-eye, with post-its closer to the center representing alters who are closer to the participant and

Figure 2: Personal network highlighting strategically positioned alters

post-its clustered together (and encircled) to represent sub-groups of alters who are close to each other (e.g., immediate family members). The bulls-eye diagrams are used as a tool for advocacy training. Using the diagram, participants identify and select strategic alters (Fig. 2), including *popular* (with many connections to other alters) and *bridging* (who connect two distinct groups of alters) alters, who can facilitate efficient transfer of norms and information in the network; and *functionally strategic alters* (e.g., community opinion leaders such as religious leaders),⁸⁵ as well as alters perceived to be at high risk for HIV. Strategically positioned and high-risk alters are highlighted in discussions about disclosure decision-making and comfort disclosing to alters, to position them for possible advocacy. In prior research,⁸⁶ including in Uganda,⁸⁰ we showed participants their diagrams to facilitate a discussion of their networks, and had little difficulty with people being able to understand these concepts.⁸⁶ In the pilot, participants were able to map their networks and select alters for prevention advocacy.

The remainder of Session 4, and **Sessions 5 through 7**, provide participants with skills, confidence and support for engaging in prevention advocacy, with education about tailoring messages differently by age, gender and relationship to the index participant; participants engage in role plays around HIV testing, condom use, PrEP, stigma, engagement in care, and ART adherence (using communication skills from [name]'s prior intervention research in sub-Saharan Africa⁵⁹), with a diverse array of targets for advocacy (e.g., women, men, sex partners, youth and family members). Participants are encouraged to bring their own role-play examples to the group, which further increases the diversity of role plays, as well as the relevance and application to their personal lives. **Session 8** provides a review of prevention advocacy skills, with additional practice and role plays, and aims to inspire a commitment to ongoing prevention advocacy.

Each session includes refreshments and is facilitated by two trained HIV-positive peer facilitators (not clinic staff or providers) with experience leading groups and HIV education. The group format facilitates an interactive process, with social reinforcement, modeling, and role plays. All sessions use sharing of experiences to build support and solidarity; group problem solving and role plays to build skills and self-efficacy; personal goal-setting for positive living, disclosure, and advocacy; and take-home activities to reinforce practice of new skills and generate personal experiences for discussion in the sessions. Role plays enable new skills to be practiced and observed, and for facilitators to assess whether skills have been mastered or whether more practice is needed. Low educational levels are common, so the take-home activities do not require writing; rather, participants are

asked to engage in an activity (e.g., disclosure, prevention advocacy) and report back. Having two weeks prior to the final two sessions allows for more time to acquire experiences with disclosure and advocacy that can then be shared in the subsequent session.

The intervention manual emphasizes that PLWH should not feel pressured to disclose or advocate with any specific alter, and that they should weigh potential risks and benefits when deciding whether to disclose or advocate with an alter. The intervention also includes training for dealing with situations when alters reveal illegal or sensitive information (e.g., same-sex sexual behavior, sex work). Training emphasizes that the goal of advocacy is to encourage protective behaviors, not to elicit or act on incriminating information. If a target discloses such behavior, participants will be trained to encourage him/her to reflect on how their behavior may be related to HIV risk and discuss ways to reduce risk. Importantly, the anti-gay and mandatory HIV testing and notification laws in Uganda do not compel citizens (or healthcare providers or researchers) to report others.

Table 1. Game Changers Session Content

Topic	Content	Take-Home Activity
1: Introduction and Stigma Reduction	
 • Introduce goals; set rules for confidentiality • Introduce and define self-stigma, prevention advocacy, and disclosure decision-making • Use discussion of stigma experiences and strategies for coping with stigma to model adaptive coping and 	Practicing Self-Compassion: Focus on a difficult experience; acknowledge and accept one's own suffering;

	promote self-compassion	offer oneself self-compassion
2: Empathy, Self-Compassion, and HIV Disclosure	
 Define empathy and self-compassion, with the aid of role plays Discuss healthy disclosure decision making; use sharing of experiences to highlight potential risks and benefits of disclosure Convey importance of establishing a basis of empathy and self-compassion, and comfort with disclosure and discussing HIV, prior to conducting prevention advocacy 	Set Personal Goals for Disclosure: Assess pros and cons of disclosure to at least one social network member, and practice initiating disclosure conversations
3: Positive Living, HIV Facts and Myths, and Introduction to Social Networks	
 Share experiences with disclosure and coping with stigma since last session; provide reinforcement and problem solving of challenges Present accurate HIV information and address common HIV myths Discuss how credible advocacy for HIV prevention requires being able to model behaviors in one's own life (positive living) Set personal goals related to positive living (e.g., adherence) Introduce the concept of social networks as key to doing advocacy 	Listing Social Network Members: In preparation for the next session, participants are asked to think about whom they consider the 20 most important people to them
4. Prevention Advocacy I	
 Share experiences with disclosure and advocacy since last session; provide reinforcement and problem solve challenges Show participants how to map their own social network and identify alters to whom they have disclosed and discussed prevention, and to whom they would like to do so Define the concept of strategically positioned alters and discuss where strategically positioned alters are in participants' network maps Use network maps and strategically positioned alters to highlight how participants can play a key role in their community through advocacy Discuss how advocacy protects others, and how PLWH are credible prevention messengers; validate fears and anxiety re: advocacy Introduce strategies for effective advocacy (teaching moments, open-ended questions, rephrasing); use role plays to build skills 	Set Personal Goals for Prevention Advocacy; Practice Prevention Advocacy: Use network map to select alters to target for disclosure and advocacy, including strategically positioned alters
5-7: Prevention Advocacy II-IV	
 Share experiences with disclosure and advocacy since last session; provide reinforcement and problem solve challenges Discuss how to support alters after they have been tested for HIV Use role playing to practice and model effective advocacy 	Same as Session 4
6: Wrap Up & Review	
 Share experiences with disclosure and advocacy since last session; provide reinforcement and problem solve challenges Use role plays to practice and model challenging scenarios Share experiences with program; Affirm commitment toward goals 	N/A

Note: All sessions (except session 1) begin with a review, and all sessions end with an uplifting song/blessing to build solidarity.

Scalability and sustainability are a concern for interventions in low resource settings, especially when they take place in the context of overcrowded clinics with overburdened staff. The social network analysis and enrollment and tracking of network alters are part of the research evaluation only, not the intervention, and would not be present in its roll out. Further, clinic providers are not involved in intervention implementation, as the intervention is facilitated by trained peers, which is common in resource limited settings. For example, HIV+ peer mothers in antenatal care clinics throughout Uganda are trained to implement an 18-session, monthly 2-hour Family Support Group program rolled out by the Ministry of Health to promote PMTCT.

